## **9.4 Study Intervention Compliance**

Threshold adherence/compliance is achieved when the enrolled participant completes all HD-tDCS/sham HD-tDCS + CT sessions and undergoes cognitive testing at 0, 3 and 6 mo. This degree of participation will allow calculation of the primary outcome, i.e. treatment completion rates.

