**Cognitive Battery**

Participants will complete a broad battery of neuropsychological tests administered by trained personnel; this comprehensive battery will include the Alzheimer's Disease Cooperative Study-Preclinical Alzheimer Cognitive Composite (ADCS-PACC), which will serve as the primary outcome measure for the future phase II trial (see Table 5). The ADCS-PACC is a composite of 4 measures with well-established sensitivity for the detection of cognitive decline in prodromal and mild dementia. The final score is determined from its components using an established normalization method; the four Z scores are then added to form the composite. Consequently, a change of 0.5 standard deviations on each component would correspond to a 2-point change on the composite. We will alternate between 3 different versions of the test in order to minimize the risk of learning effects (Donohue et al., 2014).

The ADCS-PACC emerged as a response to concerns about ceiling effects, and the insensitivity to early stage deficits and to cognitive change of more standard Alzheimer's disease measures (e.g. ADAS-Cog). The PACC is currently being used as the primary outcome measure in multiple ongoing studies of early or preclinical Alzheimer's disease (Donohue et al., 2014; Harrison, 2018).

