## 12.2 Sample Size Justification

Given the pilot nature of this study, two feasibility outcomes will be included: Consent rate and treatment completion rate. 20 patients are enough to calculate a 90% exact binomial confidence interval of (.75, 1) if all 20 are observed to complete treatment. Thus, this sample size is large enough to potentially exclude completion rates of 3/4 or lower. The pilot data from this study will provide initial estimates of the variability and the effect sizes; This information will then be used for the formal calculations of power and sample size necessary to conduct a future phase II trial.

This pilot study, if successful, would prove the feasibility of the proposed approach. Treatment completion rates of less than 75% could be reasonably excluded if all 20 patients are observed to complete treatment. Additionally, recruiting and consenting 20 patients over a period of 3 months would support the feasibility of conducting a larger-scale, 2-site, phase II trial with 120 MCI patients over a span of 5 years (i.e. approximately 32 patients/year). This would be the necessary next step in the path to using combined HD-tDCS/CCT as an intervention that could lead to tangible clinical improvements. This future trial would use a 2 X 2 factorial design that would allow for the inclusion of a 'true' control group (i.e. sham HD-tDCS/sham CCT). The stimulation period would be extended (six months instead of three) with the hope of inducing longer lasting effects that could translate into a slowing of disease progression; Accordingly, we would evaluate the effects of the intervention at 6, 12 and 18 months. MRI changes would be assessed at 12 months, as well as the effect on cerebrospinal fluid (CSF) AD biomarkers of a subset of patients. **Sample size justification for future phase II trial (N=120)**. Driven by the efficacy outcome of change in ADCS-PACC score from baseline to 12 months. We presume that 10% of these patients are lost to follow up before one year. We further presume that the main aim will be addressed by a two-sided test at the .05 level of the hypothesis that the improvement rate in the true HD-tDCS group exceeds that of the sham group. Under these assumptions there is a minimum 90% power to detect a 31% difference in improvement rates. Thus, this design has good power to find a moderate effect size of HD-tDCS treatment.

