## 12.4 Statistical Methods

**In a future phase II trial** (and for this feasibility trial as appropriate), baseline clinical and demographic characteristics will be tabulated for subjects assigned to the four treatment modes in a future 2 X 2 factorial design. Comparison of these characteristics between the four groups will be carried out with t-tests and chi-square tests. If important differences are found between the groups at baseline, the statistical analyses will be repeated after adjusting for these differences. These analyses will be considered to be supportive however.

All analyses will be done under the intent-to-treat principle as far as allowed by patient consent and follow up. All consenting patients will be followed even if noncompliant. Potentially confounding patterns of loss to follow up will be investigated via sensitivity analyses.

The primary outcome variable is efficacy, defined as improvement over time in ADCS-PACC scores from baseline to 12 mo. This will be analyzed via a standard 2 x 2 x 2 analysis of covariance, where the three two-level factors are the two treatments and MCW vs. UW-Madison site, and the continuous covariate is the value of the outcome at baseline. Explicitly,

$$\mu_i = \beta_0 + \beta_{HD-tDCS} \times I(HD-tDCS_i) + \beta_{train} \times I(train_i) + \beta_{inter} \times I(HD-tDCS_i) \times I(train_i) + \beta_{base} \times Y_{i,base},$$

where:  $\mu_i$  is the mean outcome, indexed by  $i$  for subject;  $\beta_0$  is the intercept term,  $\beta_{\text{HD-tDCS}}$  is the HD-tDCS main effect term,  $I(\text{HD-tDCS}_i)$  is an indicator variable for the  $i$ th patient taking the value of 1 if s/he received true HD-tDCS and 0 for sham;  $\beta_{\text{train}}$  is the cognitive training main effect term;  $I(\text{train}_i)$  is an indicator variable for true vs. sham cognitive training in the  $i$ th patient;  $\beta_{\text{inter}}$  is the interaction term between the two treatments, measuring their synergy;  $\beta_{\text{base}}$  is the coefficient for baseline outcome level; and  $Y_{i,\text{base}}$  is the baseline outcome level for patient  $i$ . For the primary aim the outcome would be cognitive function measured by ADCS-PACC score at 12 mo (since baseline ADCS-PACC score is included, this is formally equivalent to change in 12-mo ADCS-PACC score from baseline).

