Finally, if statistically significant improvements in neuropsychological outcome measures are shown, will conduct follow-up analyses using reliable change index (RCI) scores. The RCI allows for an assessment of the magnitude of change of scores for an individual that are not susceptible to group means and standard deviations. This process has been described in detail elsewhere (Hinton-Bayre, 2010; Maassen et al., 2009). We will use the Jacobson-Truax method with a 0.90 confidence interval, which indicates a 95% chance of true improvement for anyone who passes the threshold (Jacobson & Truax, 1991).

**Neuroimaging:** In a future larger-scale phase II trial We will perform Kruskal-Wallis tests, to determine if there are significant between group differences at 12 mo, on each of the NODDI (neurite orientation dispersion (OD) index, neurite density (or intracellular volume fraction) (Vic,), and diffusivity (FA, MD, RD) measures, as well as measures of neurodegeneration measured by cortical thickness and ASL perfusion (cerebral blood volume, mean transit time, time to peak etc). Post-hoc analyses comparing the sham group to each of the three remaining groups will be done

**using Mann-Whitney U tests. All analyses will be done with and without controlling for possible confounding factors such as age, intracranial volume, family history of AD or other dementias.**

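### Passing the 0.90 reliable change threshold does not make a person 95% likely to have truly improved; it holds false passes to about 5% when nothing has changed

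*Combined protocol and SAP*

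**What the plan says.** Near the end of section 12.4 (Statistical Methods), after the ANOVA of cognitive data, the plan adds a per-person analysis to be run only "if statistically significant improvements in neuropsychological outcome measures are shown". The rule is: "We will use the Jacobson-Truax method with a 0.90 confidence interval", "which indicates a 95% chance of true improvement for anyone who passes the threshold". The section prints no formula. It names no reliability value, no source for the standard deviation and no adjustment for practice. It describes the scores as ones "that are not susceptible to group means and standard deviations".

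Three other places bear on this:

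- **Scope.** Section 12.4 opens as the plan for a future phase II trial, "and for this feasibility trial as appropriate".
- **Number of testings.** In the pilot, section 9.4 counts as adherent a participant who completes all sessions and "undergoes cognitive testing at 0, 3 and 6 mo", which is three testings. For the later trial, section 12.2 says "we would evaluate the effects of the intervention at 6, 12 and 18 months", which with baseline makes four.
- **Practice.** The Cognitive Battery text in section 10.1 says, of the ADCS-PACC, "We will alternate between 3 different versions of the test in order to minimize the risk of learning effects". Nothing similar is stated for the tests in Table 6.

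**The concern.** The sentence takes the probability of not passing when nothing has changed and reports it as the probability of real change once a person has passed. The first is fixed by the cut-off. The second is not: it also depends on how many people truly improve and how often the rule detects them. A reader who follows the plan could describe each individual who passes as 95% certain to have benefited, a statement the analysis cannot support.

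A second, smaller matter concerns the 5% itself. In its standard form the Jacobson-Truax index divides the raw retest difference by the standard error of the difference. It contains no term for the gain expected from repeated testing, so the 5% is nominal and applies only if there is no such gain.

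**Working it through.** **Inputs from the documents.** Jacobson-Truax index, 0.90 interval, claimed 95% (section 12.4); testing at 0, 3 and 6 months (section 9.4); 20 participants, 10 per arm (section 7.1).

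**Inputs not in the documents, so assumed over ranges.** Share of true improvers p, 5% to 50%; sensitivity s, 30% to 100%; practice gain m, 0 to 1.0 standard errors of the difference; test-retest reliability r, 0.7 to 0.9.

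**Step 1: reproduce the 95%.** A two-sided 0.90 interval has cut-off 1.645. The upper tail is 1 − Φ(1.645) = 0.05, and 1 − 0.05 = 0.95. The plan's figure is recovered, but as P(does not pass as improved | no true change, no practice gain).

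**Step 2: the quantity the sentence claims.** By Bayes' rule,

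P(truly improved | passes) = p·s / [p·s + (1 − p)·0.05].

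- p = 10%, s = 30%: 0.030 / (0.030 + 0.045) = 0.40
- p = 30%, s = 70%: 0.210 / (0.210 + 0.035) = 0.857
- p = 50%, s = 80%: 0.400 / (0.400 + 0.025) = 0.941

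Over the wider assumed ranges:

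| True improvers | s = 30% | s = 50% | s = 80% | s = 100% |
|---|---|---|---|---|
| 5% | 0.240 | 0.345 | 0.457 | 0.513 |
| 10% | 0.400 | 0.526 | 0.640 | 0.690 |
| 20% | 0.600 | 0.714 | 0.800 | 0.833 |
| 30% | 0.720 | 0.811 | 0.873 | 0.896 |
| 50% | 0.857 | 0.909 | 0.941 | 0.952 |

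**Step 3: what 95% would require.** Setting the expression to 0.95 gives p = 0.95 / (0.95 + s). True improvers would have to make up 49% at perfect sensitivity, 54% at 80%, 66% at 50% and 76% at 30%.

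**Step 4: the nominal 5% and practice.** With an uncorrected gain of m standard errors of the difference, the false-pass rate is 1 − Φ(1.645 − m):

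- m = 0.25: 8.2%
- m = 0.5: 12.6%
- m = 1.0: 26.0%

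In baseline SD units the standard error of the difference is SD·√[2(1 − r)]. A gain of 0.25 SD then gives 9.3%, 10.6% or 13.9% at r = 0.7, 0.8 or 0.9.

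**Step 5: per test and per follow-up.** Two follow-ups against one shared baseline have change scores correlated 0.5. By simulation, the chance of passing at one or both is about 8.7% per test with no true change and no practice gain.

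**Step 6: counts.** If all 20 pilot participants were unchanged, 20 × 0.05 = 1 would be expected to pass per test and follow-up. If 10-30% truly improved, 14 to 18 are unchanged and the expected number of false passes is 0.7 to 0.9.

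**The case against.** The strongest reply accepts that the sentence is wrong and disputes how much follows from it.

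- **Scope.** The paragraph follows an ANOVA with four groups and an adherence rule at 12 months, neither of which fits a two-arm, six-month pilot. The reliable change analysis is in neither endpoint list (sections 6.0 and 12.1). This stands: the pilot uses the analysis only as appropriate, and the wording error is the same in either trial.
- **The trigger.** The scores are computed only after a significant group result, which makes a larger share of true improvers more plausible. That is fair, and it is why the 94% case is shown beside the lower ones. A significant group mean still does not fix the individual probability at 95%.
- **Practice.** A reader might infer that the 5% definitely fails and that many who pass merely show practice. The documents do not support that. They report no practice gain, and the ADCS-PACC uses three alternating versions. Section 5.1 describes a population progressing to Alzheimer disease at 10 to 15% per year, and expected decline acts the other way: a fall of 0.25 standard errors would give 1 − Φ(1.895) = 2.9%. What stands is that the index has no practice term and that alternate forms are stated only for the ADCS-PACC.
- **Group standard deviations.** A reader might also call the plan's remark about group means and SDs plainly false, because the denominator uses an SD and a reliability. The plan does not say where these come from. External norms would not depend on this trial's groups, and the remark may only contrast individual change with tests of group means. It is not pressed here.

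**Conclusion.** The clause is wrong as written, and showing this needs no assumption: a 5% false-pass rate is not a 95% probability of real improvement after a pass. The size of the gap does rest on assumptions. It is large if few people improve (40% at 10% improvers and 30% sensitivity) and almost nil if half improve and sensitivity is high (94% at 50% and 80%). The practice figures of 8% and 13% are likewise conditional on assumed gains.

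A reader might infer that the pilot's conclusions are compromised. They are not: the primary endpoint is treatment completion, and practice common to both arms largely cancels when arms are compared. What changes is what may be said about individuals.

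**What to change.** 1. Replace the clause in section 12.4 with: if there is no true change and no practice gain, about 5% are expected to pass in the improving direction, per test and per follow-up.
2. Do not describe individuals who pass as 95% likely to have truly improved.
3. Either state that the index makes no allowance for practice or, wherever pass rates are reported, show them by arm.
4. Do not present subtraction of the pilot sham-arm mean change as a pure practice correction. Under sections 7.1 and 9.1 that arm receives active cognitive training, so its mean change mixes practice with any training effect. The adjusted score would mean change beyond sham stimulation plus training, and should be labelled so. It would also be imprecise: with about 10 subjects the standard error of that mean is 1/√10 = 0.32 of the SD of change. If that SD is close to the standard error of the difference, this exceeds the 0.25 shift in the example above. The group given sham stimulation and sham training in the future factorial trial (section 12.2) would be a cleaner reference.

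The cost is one reworded clause and, if pass rates are reported, a split by arm of data already collected. The price is a weaker claim about individuals.

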## 12.5 Planned Interim Analysis

There will not be an interim analysis.

## 13.0 RISK/BENEFIT ASSESSMENT

### 13.1 Potential Benefits to the Subjects

There are no direct benefits to participating in the study. The scientific benefits are great and include a better understanding of the associations between the planned interventions and brain/biomarker/cognitive changes associated with MCI and Alzheimer's disease and possible mechanisms underlying these associations. Study completion may provide evidence in support of HD-tDCS + CT as an efficacious approach to the prevention of Alzheimer's disease and related neurodegenerative disorders in midlife.

### 13.2 Known Potential Risks

**MRI:** Participants are screened by study staff prior to the scan to verify they do not have any contraindications for MRI. Potential side effects of the scan include anxiety due to claustrophobia and/or noise. Participants with known anxiety or claustrophobia will not be recommended to participate since the head must be placed fully inside the MRI scanner tube. If a participant experiences anxiety, they will be removed from the scanner and offered reassurance by study staff. To minimize the level of noise, all subjects will be fitted with disposable earplugs. Communication with the participant is possible during the scan. In addition, fatigue and physical discomfort due to the length of the scan session are possible. Participants will be reminded that the procedure is optional.

The MRI scanner to be used in the study is considered an investigational device due to the investigational software and equipment used in the study (for blood flow imaging), which is being supplied by GE; however, the baseline Magnetic Resonance Imaging (MRI) device is an FDA cleared device for safely and non-invasively imaging the interior of the human body. The scanner restricts research software from exceeding FDA safety levels. Thus, the scanner with the investigational software and equipment fully engaged operates, from a technical design and functional standpoint, as a **non-significant risk** device in accordance with 21 CFR 812.

**Risks of extended neuropsychological testing:** Extended neuropsychological testing may cause embarrassment, sadness when asked about personal feelings. The subject may feel bored, nervous, embarrassed with some of the tests or when answering questions about how he/she feels.

**Risk of Breach of Confidentiality:** Because personal information will be retained in a computer database, there is a small possibility that this information could become available to unauthorized persons. This study involves protections to minimize the chance of any such breach.

### Known Interventional Risks

Risks of HD-tDCS include redness and skin irritation at the site of stimulation. When current flow is initiated the subject may perceive a tingling sensation on his/her scalp. In one study, fatigue was reported as a side effect of tDCS. Turski et al (2017) reported that one subject developed a headache during one session, which resolved when stimulation was stopped. Another subject reported poor sleep one night, which however resolved and was judged to not be caused by the stimulation.

### 13.3 Risk/Benefit Analysis

The risks of the proposed procedures are minimal, and the potential knowledge gains are substantial, making the risk/benefit ratio low. These experiments will provide a unique opportunity to determine the potential for HD-tDCS and CT to benefit participants with MCI.

## 14.0 DATA AND SAFETY MONITORING

### 14.1 Adverse Event (AE) Definition

Adverse event (AE) means any untoward medical occurrence associated with the use of an intervention in humans, whether or not considered intervention-related.

### 14.2 Serious Adverse Event (SAE) Definition

An adverse event is considered "serious" if, in the view of either the investigator or sponsor, it meets any of the following criteria:

- Results in death
- Is life-threatening
- Requires an inpatient hospitalization or prolongation of an existing hospitalization
- Results in persistent or significant disability or incapacity.
- Results in a congenital anomaly/birth defect.
- A medical event, based on appropriate medical judgment, that is believed to jeopardize the subject and/or requires medical or surgical intervention to prevent one of the outcomes defining a SAE. For example: allergic bronchospasm requiring intensive treatment in an emergency room or at home, convulsions that may not result in hospitalization

### 14.3 Classification of an Adverse Event

#### Severity of Event

All AEs will be assessed by the clinician using the Common Terminology Criteria for Adverse Events (CTCAE), version 5.0, each event searchable using the Safety Profiler website (<https://safetyprofiler-ctep.nci.nih.gov/CTC/CTC.aspx>). For AEs not included in the protocol-defined grading system, the following guidelines will be used to describe severity.

Mild (Grade 1)	Events require minimal or no treatment and do not interfere with the subject's daily activities.
Moderate (Grade 2)	Events result in a low level of inconvenience or concern with the therapeutic measures. Moderate events may cause some interference with functioning.
Severe (Grade 3)	Events interrupt a subject's usual daily activity and may require systemic drug therapy or other treatment. Severe events are usually potentially life-threatening or incapacitating.
Life Threatening (Grade 4)	The subject was at risk of death at the time of the event.
Fatal (Grade 5)	The event caused death.

### Relationship to Study, Study Procedure(s) and/or Study Intervention(s)

For all collected AEs, the clinician who examines and evaluates the subject will determine the AE's causality based on temporal relationship and his/her clinical judgment. The degree of certainty about causality will be graded using the categories below.

Definitely Related	Clearly related to the study procedures/intervention and other possible contributing factors can be ruled out.
Probably Related	Likely related to the study procedures/intervention and the influence of other factors is unlikely.
Possibly Related	Possibly related to the study procedures/intervention and there are other factors that could be equally likely.
Unlikely to be related	Doubtfully related to the study procedures/intervention and there is another likely cause.
Unrelated	Clearly not related to the study procedures/intervention and/or evidence exists that the event is definitely related to another cause.

### Expectedness for Study, Study Procedure(s) and/or Study Intervention(s)

The PI will be responsible for determining whether an AE is expected or unexpected in relation to the study procedures and intervention(s) (as applicable).

For device studies: An AE will be considered unexpected if the nature, severity, or frequency of the event is not consistent with the risk information previously described in the clinical protocol, device manual, investigator's brochure, the package insert(s), the IRB application, or the informed consent document. Expectedness is recorded for both study procedures and interventions.

### 14.4 Time Period and Frequency for Event Assessment and Follow-Up

The occurrence of an AE or SAE may come to the attention of study personnel during study visits and interviews of a study subject presenting for medical care, or upon review by a study monitor. All AEs including local and systemic reactions not meeting the criteria for SAEs will be captured on the appropriate CRF. Information to be collected includes event description, time of onset, clinician's assessment of severity, relationship to study product (assessed only by those with the training and authority to make a diagnosis), and time of resolution/stabilization of the event. All AEs occurring while on study must be documented appropriately regardless of relationship. All AEs will be followed to adequate resolution.

Any medical condition that is present at the time that the subject is screened will be considered as baseline and not reported as an AE. However, if the study subject's condition deteriorates at any time during the study, it will be recorded as an AE.

Changes in the severity of an AE will be documented to allow an assessment of the duration of the event at each level of severity to be performed. AEs characterized as intermittent require documentation of onset and duration of each episode.

The PI will record all reportable events with start dates occurring any time after the administration of the study drug and for up to 30 days after the date of the last dose of study drug. At each study visit, before and after each interventional session, the investigator will inquire about the occurrence of AE/SAEs since the last contact. Events will be followed for outcome information until resolution, stabilization, or completion of study participation.

